9.7.1.1. Analysis Populations

9.7.1.1.1. Populations

The Full Analysis Set (FAS) consists of all subjects [REDACTED]. Subjects will be analyzed in the group to which [REDACTED]. This set will be used for the analysis of all efficacy endpoints.

The Safety Analysis Set will include all subjects who took at least one dose of double-masked investigational product as indicated on the dosing record. Subjects will be analyzed in the group according to the treatment received. All safety variables will be analyzed using the Safety Analysis Set and only observed data will be included (i.e., missing data will remain missing for the safety analysis). If the safety analysis set is the same as the FAS, then safety results will be provided using the FAS.

9.7.1.1.2. Analysis Eyes

Subjects in the FAS will have at least one eye that qualifies based on the criteria in the protocol. Both eyes may qualify based on the criteria.

Efficacy analyses will be performed in the study eye and non-study eyes.

The study eye is defined as the eye meeting all inclusion criteria and no exclusion criteria, and with the highest tCFS scoring at randomization (Visit 2, Day 1). If both eyes meet the inclusion criteria and no exclusion criteria and have the same tCFS score, the right eye will be used as the SE.

Safety analyses will be presented for both eyes.

9.7.1.2. Analysis of Subject Disposition

The number of subjects randomized at each site will be summarized by treatment group and overall.

Subjects' enrollment and disposition during the study will be summarized by treatment group and overall using Randomized Subjects. The reasons for discontinuation will be displayed in the order as they appear on the eCRF.

The summary table will include the following. The percentages will be calculated based on the number of subjects randomized. For reason for discontinuation from study, percentages are based on the number of subjects who discontinued the study.

- Number of subjects screened
- Number and percentage of subjects randomized
- Number and percentage of subjects randomized with any protocol deviation
- Number and percentage of subjects treated
- Number and percentage of subjects treated with any protocol deviation
- Number and percentage of subjects in the Safety, Full, and Per Protocol Analysis Sets
- Number and percentage of subjects treated who completed the study
- Number and percentage of subjects treated who discontinued from the study
- The reasons for study discontinuation
- Number and percentage of subjects attending each scheduled study visit.

A listing of subjects who do not meet all inclusion criteria or meet exclusion criteria will be provided.

9.7.1.3. Analysis of Demographic and Baseline Characteristics

9.7.1.3.1. Demographics and Disease Characteristics

Demographic characteristics including age (years), age group (<65 years, \geq 65 years), sex, race, ethnicity, qualifying eyes (1 or 2), study eye (OD/OS), and baseline tCFS score

MMP-9, and

will be summarized descriptively by treatment group and overall using the FAS and Safety Analysis Sets. For categorical parameters, the percentages will be calculated overall and based on the number of subjects in each treatment group based on non-missing observations. The baseline characteristic parameters will be summarized for both the study eye and the non-study eye if the assessments were done on each eye separately.

9.7.1.3.2. Medical History

Medical history will be coded using the Medical Dictionary for Regulatory Activities (MedDRA Version 25.0, Mozzicato, 2009). The frequency and percentage of subjects with any medical history will be summarized by treatment group using the FAS. System organ class (SOC) will be sorted alphabetically and preferred term (PT) within each SOC will be sorted by overall descending order of frequency according to the following rules in order:

1. Descending frequency within SY-201, 2.0%;
2. Descending frequency within SY-201, 1.0%;
3. Descending frequency within SY-201, 0.5%;
4. Descending frequency within Vehicle;
5. PT in alphabetical order.

The medical history will include both the ocular and the general (non-ocular) history. Ocular medical history and general (non-ocular) medical history will be summarized separately. Ocular and non-ocular medical histories are identified according to which CRF the event is recorded. Ocular medical history will be summarized separately for study eye, non-study eye, and either eye.

9.7.1.3.3. Prior and Concomitant Medications

Prior and concomitant medications will be coded using the World Health Organization Drug Dictionary (WHODrug) (Version 2022-03, Lagerlund et al., 2020) for anatomical therapeutic chemical (ATC) classification and preferred drug name.

The frequency and percentage of subjects with coded medications will be summarized by treatment group using the Safety Analysis Set. A subject who used multiple medications will be counted only once for each ATC and preferred drug name. Therapeutic Subgroup is sorted alphabetically, and preferred term is sorted by descending frequency overall within each Level 3 term according to:

1. Descending frequency within SY-201, 2.0%;
2. Descending frequency within SY-201, 1.0%;
3. Descending frequency within SY-201, 0.5%;
4. Descending frequency within Vehicle;
5. PT in alphabetical order.

Prior and concomitant medications will be summarized separately. Ocular medications are defined as those medications for which an eye has been specified (OD, OS, or OU). Ocular and non-ocular medications will be summarized separately. Ocular medications will be summarized separately for study eye, non-study eye, and either eye.

Prior medications are defined as any medications that started and stopped prior to the first dose of double-masked study drug. Concomitant medications are defined as any medications that (1) start prior to the first dose of double-masked study drug and stop or are ongoing at or after the date of first dose of double-masked study drug; or (2) start at or after the first dose of double-masked study drug. Medications taken after Visit 6 or withdrawal from the study are not considered concomitant.

9.7.1.4. Analysis of Study Medication Compliance and Exposure

The overall treatment compliance and exposure will be assessed by the data from the in-clinic administration, IP accountability, and study completion eCRFs and will be summarized by treatment group using the Safety Analysis Set.

The total number of doses of double-masked study drug that were taken will be calculated as the number of used vials returned to the clinic. Each single use vial contains product for one OU dose.

Treatment compliance for double-masked study drug is defined as the proportion of doses taken out of the expected number of doses for the double-masked treatment period. The overall compliance (%) will be calculated as (total number of doses taken / expected number of doses) \times 100. The expected number of doses is defined as doses per day \times days in double-masked treatment period, i.e., $[2 \times (\text{last double-masked dose date} - \text{first double-masked dose date} + 1)]$. Last double-masked dose date will be taken from the study completion eCRF. Since the expected number of doses is based on last dose, compliance is adjusted for the early withdrawals. Treatment compliance for the run-in period is defined as (total number of doses taken / expected number of doses) \times 100 where the expected doses are $[2 \times (\text{Visit 2 date} - \text{Visit 1 date})]$.

Duration of exposure of double-masked study drug will be calculated as the total number of days from the first double-masked dose date to the last double-masked dose date plus 1 (one) regardless of temporary dose interruptions.

Total number of doses of double-masked study drug that were taken, compliance, and the duration of exposure to double-masked study drug (days) will be summarized by descriptive statistics. The frequency and percentage of subjects in the following study drug compliance categories ($\geq 80\%$, $< 80\%$) will be summarized by treatment group. The percentages will be calculated based on the number of non-missing observations in each treatment group of the Safety Analysis Set. No inferential statistics will be calculated.

Total number of doses of single-masked run-in drops taken, duration (in days), compliance, and compliance categories ($\geq 80\%$, $< 80\%$) during the run-in period will be summarized by treatment group based on Safety Analysis Set. No inferential statistics will be calculated.

9.7.1.5. Analysis of Efficacy

Summary descriptive statistics will be presented for all study visits at which efficacy data are collected. Efficacy analyses will be presented by the study eye and non-study eyes.

For subjects who discontinue treatment prior to Visit 6, data collected using Early Termination eCRFs will not be summarized separately unless the termination occurred on a scheduled visit (within the visit windows of a particular visit).

All longitudinal models will be fit using the MIXED procedure in SAS. Categorical analyses will be conducted using the FREQ procedure.

All efficacy analyses will be conducted using the FAS Analysis Sets.

To control for type I error, comparisons will be made within each active dose level of SY-201 Ophthalmic Solution compared to Vehicle. In other words, the primary endpoints will be compared sequentially between SY-201 Ophthalmic Solution [REDACTED] and Vehicle, first testing tCFS and, if statistically significant, [REDACTED]. Should both endpoints achieve statistical significance

for the [REDACTED] testing will proceed to SY-201 Ophthalmic Solution [REDACTED] versus Vehicle, first testing tCFS and, if statistically significant, [REDACTED]. Should both endpoints achieve statistical significance for the [REDACTED] testing will proceed to SY-201 Ophthalmic Solution [REDACTED] and Vehicle, first testing tCFS and, if statistically significant, [REDACTED]. In other words, the first non-significant result in this testing hierarchy of six hypotheses will imply that subsequent tests are non-significant.

Testing of all active doses combined compared to vehicle will also be performed.

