For analysis of efficacy endpoints, longitudinal models will model the change from baseline of each endpoint as the dependent variable with the baseline measurement of the corresponding endpoint as a covariate and treatment group as the main effect. A random effect for site will be added to account for site-to-site variability.

Subgroups

Subgroup analyses will include testing of the mean CFB in tCFS,

Subgroup analyses by sex and age group (<65 years, ≥65 years) may also be performed.

Multiplicity

To control for type I error, comparisons will be made within each active dose level of SY-201 Ophthalmic Solution compared to Vehicle. In other words, the primary endpoints will be compared sequentially between SY-201 Ophthalmic Solution 2.0% and Vehicle, first testing tCFS and, if statistically significant, . Should both endpoints achieve statistical significance for the 2.0% dose, testing will proceed to Y-201 Ophthalmic Solution 1.0% versus Vehicle, first testing tCFS and, if statistically significant, . Should both endpoints achieve statistical significance for the 1.0% dose, testing will proceed to SY-201 Ophthalmic Solution 0.5% and Vehicle, first testing tCFS and, if statistically significant, . In other words, the first non-significant result in this testing hierarchy of six hypotheses will imply that subsequent tests are non-significant.

Missing Data and Outliers

Every attempt will be made to capture all study data. All analyses will utilize observed data only. Analysis of continuous efficacy endpoints using MMRM assumes missing at random (MAR). Sensitivity analyses of the primary endpoints will be performed utilizing control-based pattern imputation, last observation carried forward (LOCF), and baseline observation carried forward (BOCF).

Visit Windows

The nominal visits listed in the eCRF will be used in the summaries. In general, unscheduled visits will not be summarized in tables unless otherwise noted.

Missing Dates

Missing dates that occur for prior or concomitant medications or adverse events will be queried for a date. If no date is obtained, the following imputation rules will apply:

- For start dates, if the given year (or year-month) is the same as study drug administration, the start date will be imputed as study drug administration date; otherwise, missing month-day (or day) will be imputed as '01-01' (or '01').

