9.7.1.5.1. Primary Efficacy Analysis

Primary Estimands: The primary estimands are the treatment differences between SY-201 Ophthalmic Solution arms and vehicle for mean CFB to Day 60 in tCFS using study eyes and mean CFB to Day 60 in eye [REDACTED] using the FAS.

Target Population: Subjects with DED who meet the study entry criteria.

Endpoints: Change from baseline at Day 60 for tCFS using study eyes and change from baseline at Day 60 for eye dryness score.

Treatment Condition(s): Treatment condition is based on the randomized treatment group.

Population-level Summaries: The difference in the mean CFB to Day 60 in tCFS using study eyes and the difference in mean CFB to Day 60 in eye dryness score and their p-values and corresponding 95% confidence intervals.

The proposed procedures to handle missing data and intercurrent events are as follows:

- Discontinuation of study therapy with continued participation in the study
 - Treatment Policy – no imputation; use observed data
- Receipt of rescue therapy
 - Treatment Policy – no imputation; use observed data
- Missing data with or without withdrawal, regardless of reason
 - Hypothetical approach – missing data will be accounted for assuming missing at random (MAR) using mixed-model repeated measures (MMRM).

Mean CFB in tCFS will be analyzed using a MMRM model. The model will include the baseline measurement, treatment, time, and treatment by time interaction as fixed effects, with a random effect for site. An unstructured covariance among repeated measurements is assumed. A similar model for the subject-level mean CFB in eye dryness score will be used.

Sample repeated measures model code:

```
PROC MIXED DATA=indata;
  CLASS subject center visit treatment(REF='Vehicle');
  MODEL change = baseline_value visit treatment visit*treatment / Solution DDFM=KR;
  REPEAT visit / SUBJECT=subject TYPE=UN;
```

```
RANDOM center;
LSMEANS treatment*visit / slice = visit DIFF CL;
RUN;
```

If the model fails to converge using this covariance structure, spatial power or compound symmetry will be implemented in this order.

Sensitivity analyses of the primary endpoints will be performed utilizing control-based pattern imputation, last observation carried forward (LOCF), and baseline observation carried forward (BOCF).

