9.7.2. Determination of Sample Size

For mean change from baseline to Day 60 in tCFS, a sample size of 45 SY-201-treated subjects versus 45 vehicle-treated subjects will have 87.9% power to detect an effect size of 2.0 units with a standard deviation of 3.0 for an unpaired t-test with a 2-sided alpha = 0.05. For mean change from baseline to Day 60 in dry eye symptom , a sample size of 45 SY-201-treated subjects versus 45 vehicle-treated subjects will have 83.5% power to detect an effect size of 1.5 units with a standard deviation of 2.4 for an unpaired t-test with a 2-sided alpha = 0.05.

Fifty (50) subjects per treatment arm, for a total 200 subjects, will be enrolled to allow for some dropout of subjects.

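### Binary efficacy endpoints, if compared between arms, are assigned to PROC FREQ, which cannot use the continuous baseline score; a baseline-adjusted logistic model would be a cheap, modest gain in power

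*SAP*

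**What the plan says.** SAP section 9.7.1.5 (Analysis of Efficacy) assigns software by type of analysis. Longitudinal models go to PROC MIXED, and "Categorical analyses will be conducted using the FREQ procedure". The visible text names no test, stratification factor or covariate for the categorical analyses.

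The Strata and Covariates paragraph of SAP section 9.7.1 treats the continuous analyses differently. There, "longitudinal models will model the change from baseline of each endpoint as the dependent variable with the baseline measurement of the corresponding endpoint" serving for adjustment, and site enters as a random effect. That paragraph mentions no categorical analysis.

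Both primary endpoints are continuous. SAP section 9.7.1.5.1 says "Mean CFB in tCFS will be analyzed using a MMRM model" and "A similar model for the subject-level mean CFB in eye dryness score will be used". The six-test hierarchy and the sample size (SAP section 9.7.2) concern these two endpoints only.

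The secondary endpoints and their analyses (SAP section 9.7.1.5.2; protocol sections 2.2.2 and 9.4.2.2) are blank in the public text, so no categorical efficacy endpoint can be seen.

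**The concern.** PROC FREQ produces contingency-table tests: chi-square, Fisher's exact test or, with strata, CMH. None of these takes a continuous covariate. For a responder endpoint built on a scored measure, the chance of reaching the threshold may well depend on the starting score, and that score is collected in every subject before the first double-masked dose. Leaving it out costs power whenever it is prognostic, and chance baseline imbalance in arms of about 45 goes uncorrected.

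What is at stake is the efficiency of a secondary comparison. The validity of the trial is not in question.

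**Working it through.** **Reproducing the plan's power.** SAP section 9.7.2 uses "a sample size of 45 SY-201-treated subjects versus 45 vehicle-treated subjects", "for an unpaired t-test with a 2-sided alpha = 0.05". The standard error is SD × √(2/45), with 88 degrees of freedom.

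- tCFS: 3.0 × 0.2108 = 0.632; noncentrality 2.0/0.632 = 3.16; power 87.9%, as stated.
- Symptom score: 2.4 × 0.2108 = 0.506; noncentrality 1.5/0.506 = 2.96; power 83.5%, as stated.

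Both figures reproduce, and neither depends on the FREQ sentence. The plan gives no power or response rate for a categorical endpoint, so the rest is illustration.

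**Inputs for the illustration.**

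- From the SAP: 45 per arm, tCFS difference 2.0, SD of change 3.0, two-sided 0.05.
- Assumed: vehicle mean improvement 1 unit; response defined as improvement of at least 2 or at least 4 units; correlation ρ between baseline and improvement (that is, −ρ with change from baseline).

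The response rates follow from 1 − Φ((cut-off − mean)/3):

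- Cut-off 2: vehicle 1 − Φ(0.33) = 37%; active 1 − Φ(−0.33) = 63%.
- Cut-off 4: vehicle 1 − Φ(1) = 16%; active 1 − Φ(0.33) = 37%.

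**Power (%), 3,000 simulated trials per row.** CMH is stratified at the median baseline. Logistic is the likelihood-ratio test of treatment in a model with baseline.

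| ρ | Cut-off | Chi-square | CMH | Logistic | Logistic − chi-square | Logistic − CMH |
|---|---|---|---|---|---|---|
| 0 | 2 | 70.5 | 70.9 | 71.9 | 1.4 | 1.0 |
| 0 | 4 | 64.8 | 63.0 | 64.2 | −0.6 | 1.2 |
| 0.3 | 2 | 68.1 | 70.0 | 72.2 | 4.1 | 2.2 |
| 0.3 | 4 | 64.9 | 64.3 | 66.3 | 1.4 | 2.0 |
| 0.5 | 2 | 69.3 | 76.0 | 78.7 | 9.4 | 2.7 |
| 0.5 | 4 | 64.8 | 67.2 | 70.8 | 6.0 | 3.6 |
| 0.7 | 2 | 69.2 | 81.1 | 85.2 | 16.0 | 4.1 |
| 0.7 | 4 | 64.1 | 70.4 | 79.9 | 15.8 | 9.5 |

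The Monte Carlo standard error of one power figure is about √(0.7 × 0.3/3000) = 0.8 point.

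A second setting assumes vehicle improvement 1.5 and cut-offs 3 and 4. At ρ = 0.6 it gives chi-square 67% to 70%, CMH 76% and 73%, and logistic 80% and 78%. Over all settings run, the gain of logistic over chi-square is about 0 at ρ = 0, 1 to 5 points at 0.3, 6 to 10 at 0.5 and 10 to 13 at 0.6.

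**Type I error (no treatment difference, same settings as the table).** Chi-square 5.0% to 6.2%, CMH 4.7% to 5.4%, logistic 5.2% to 6.5%. In matched rows logistic exceeds chi-square by at most 0.9 point (6.2% against 5.3%), so a small part of its gain is a slightly liberal test.

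**Which ρ is plausible?** The documents do not say. If baseline and Day 60 scores have equal spread and correlation r, the correlation of baseline with change is −√((1 − r)/2). This is −0.59 for r = 0.3, −0.50 for r = 0.5 and −0.39 for r = 0.7. Entry criteria that narrow the baseline spread would weaken it.

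**The case against.** The strongest objection is that the decisive text cannot be seen. SAP section 9.7.1.5.2, where a test and its strata would be expected, is redacted, and naming a SAS procedure is not naming a test. PROC FREQ can run CMH stratified by baseline category, which recovers part of the loss. The sentence may not even govern hypothesis tests: the safety sections on BCVA and IOP call simple threshold counts a categorical analysis, and SAP section 9.7.1.6 plans no treatment comparisons there unless specified. All of this stands. It limits the point to what PROC FREQ cannot do whatever the hidden text says, which is to use baseline as a continuous covariate.

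Three stronger readings are tempting, and the documents do not support them:

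- A reader might infer that the categorical comparisons ignore baseline altogether. That would count redacted text against the plan.
- A reader might add a missing-data complaint, since "All analyses will utilize observed data only". The rule for the redacted endpoints cannot be seen, and a Day 60 logistic model would also drop subjects without a Day 60 value. Changing to logistic regression does not settle that issue.
- A reader might say that a responder result could disagree with the MMRM only because of the test chosen. Dichotomising alone takes the same tCFS effect from 87.9% power to about 65% to 70% at ρ = 0. The two analyses also differ in endpoint and in handling of missing visits.

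The size is also open to challenge, because it rests on assumed responder definitions and correlations and is about nil at ρ = 0.

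**Conclusion.** The point holds as a minor efficiency matter. The visible SAP assigns categorical efficacy analyses to a procedure that cannot use the continuous baseline, while the longitudinal models do use it. It matters only for a binary efficacy endpoint that is compared between arms and has a baseline value of the same measure.

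For such an endpoint, an unadjusted test could forgo anything from nothing to about 13 power points over correlations of 0 to 0.6. If the redacted section already specifies a baseline-stratified CMH test, less is lost: about 3 to 4 points at a correlation of 0.5. These figures rest on the assumed vehicle change, cut-offs and correlation, not on anything the documents report. An unadjusted test remains valid, with type I error near 5%, and no primary or powered comparison changes.

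**What to change.** Replace the FREQ sentence in SAP section 9.7.1.5 with:

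> Binary efficacy endpoints compared between treatment groups will be analysed by logistic regression with treatment and the baseline value of the corresponding measure, reporting the standardised difference in proportions versus vehicle with its 95% CI. PROC FREQ will supply counts and percentages, and an exact or baseline-stratified CMH test if the model does not converge.

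A random site effect need not be required here; it was not part of the model checked above.

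The cost is SAP wording and a little programming, with no new data. There are three downsides. The odds ratio is conditional on baseline, which is why the standardised difference is reported; the coverage of its interval was not simulated. The likelihood-ratio test is slightly liberal in arms of this size. Sparse responses need the stated fallback. The change belongs before unmasking.

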9.7. STATISTICAL METHODS PLANNED IN THE PROTOCOL AND DETERMINATION OF SAMPLE SIZE

This section of the analysis plan describes the analyses explicitly mentioned in the protocol as well as additional analyses not explicitly mentioned in the protocol but planned prior to breaking the treatment mask. [Section 9.8](#) describes any changes to analyses that were explicitly mentioned in the protocol or statistical analysis plan.

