9.7.1. Statistical and Analytical Plans

General Conventions

Summary statistics for the data collected during this study will be presented to give a general description of the subjects studied. Data from all sites will be combined in the computation of these descriptive summaries. Categorical variables will be summarized by the frequency and percentage of subjects in each category. Continuous variables will be summarized using N, mean, standard deviation (SD), median, minimum, and maximum values.

Number of subjects, minimums, and maximums will be calculated to the same number of decimal places as the source data. Means, medians, standard deviations, and quartiles will be calculated to one more decimal place than the source data. Percentages will be calculated to the nearest one decimal place. Zero count cells will be displayed as "0" with percentage of (0%). Unless otherwise noted, summaries will be performed by the treatment group and presented in the order of: SY-201 2.0% or 1.0% or 0.5% (efficacy analyses only), SY-201, 2.0%; SY-201, 1.0%; SY-201, 0.5%; Vehicle.

Statistical tests will be presented as two-sided p-values rounded to four decimal places; p-values less than 0.0001 will be presented as '<0.0001' and p-values = 1 will be presented as '>0.9999' in all tables. Unless otherwise indicated, statistical testing will be carried out at the $\alpha = 0.05$ significance level.

Baseline values will be defined as the last measurement prior to dosing of double-masked study medication. Ocular measurements will use the most recent measurement for each eye.

Numeric laboratory data may be recorded at limits of detection (with a '<' or '>' sign, i.e. < 0.1 or > 0.1). To summarize the data, the original value will be converted to one unit less or more at the level of measured precision (e.g. 0.4 in the case of < 0.5 and to 0.6 in the case of > 0.5). The actual values will be presented in the data listings.

MMP-9 data may be recorded at limits of detection of < 5 ng/mL or > 1000 ng/mL. To summarize the data, the original value will be converted to either 4 ng/mL or 1010 ng/mL, respectively. The actual values will be presented in the data listings.

All data collected in this study will be presented in individual subject data listings for all subjects.

Computations for all results will be performed using SAS (Version 9.4, SAS/STAT 15.2) computer software package (SAS Institute, Inc, 2013, 2020), unless otherwise specified.

Strata and Covariates

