Control-based pattern imputation would be performed using code similar to the below. The first call is to ensure a monotone missing data pattern. The second call is to perform the control-based pattern imputation.

```
PROC MI DATA=indata SEED= OUT=monotone MINIMUM=0 0 0 0 0 MAXIMUM=4 4 4 4 4 ROUND=0.5
NIMPUTE=25;
  MCMC IMPUTE = MONOTONE;
  VAR value_V2 value_V3 value_V4 value_V5 value_V6;
RUN;

PROC MI DATA=monotone SEED= OUT= MINIMUM=. 0 0 0 0 0 MAXIMUM=. 4 4 4 4 4 ROUND=0.5
NIMPUTE=1;
  by _imputation_;
  CLASS treatment;
  VAR value_V2 value_V3 value_V4 value_V5 value_V6;
  MONOTONE reg(/details);
  MNAR model(value_V3 value_V4 value_V5 value_V6 / modelobs= (treatment = 'vehicle'));
RUN;
```

Comparisons among individual arms will be obtained from the lsmeans statement. Comparisons between the combined SY-201 arm and Vehicle (least-squares means, treatment differences, 95% confidence intervals, and p-values) will be obtained using estimate statements. Assume treatments are ordered:

1. SY-201 2.0%;
2. SY-201 1.0%;
3. SY-201 0.5%;
4. Vehicle.

And visits 3, 4, 5, and 6 are ordered numerically. Let $n_{2.0\%}$, $n_{1.0\%}$, and $n_{0.5\%}$ be the total number of subjects for the appropriate arms in the respective analysis set (FAS or Per Protocol). Define

$$p_{2.0} = \frac{n_{2.0\%}}{n_{2.0\%} + n_{1.0\%} + n_{0.5\%}} \text{ with } p_{1.0} \text{ and } p_{0.5} \text{ defined similarly.}$$

To generate the estimates for the combined SY-201 for Visit 3, see the below code for an example for Visit 3.

```
estimate 'SY-201 Average V3'
  intercept      1
  baseline       <<overall average at baseline for all subjects>>
  visit          1 0 0 0
  treatment      p2.0 p1.0 p0.5 0
```

```
visit*treatment p2.0 p1.0 p0.5 0 0 0 0 0  
0 0 0 0 0 0 0 0;  
  
estimate 'SY-201 Average minus Vehicle V3'  
treatment p2.0 p1.0 p0.5 -1  
visit*treatment p2.0 p1.0 p0.5 -1 0 0 0 0  
0 0 0 0 0 0 0 0;
```

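### Does the pooled-dose versus vehicle test, which has no stated place in the six-step sequence, undermine the control of type I error?

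*SAP*

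**What the plan says.** The multiplicity text in SAP 9.7.1, repeated in 9.7.1.5, tests 2.0%, then 1.0%, then 0.5% against vehicle. Within each dose tCFS comes first and the symptom score second. It closes with the rule that "the first non-significant result in this testing hierarchy of six hypotheses will imply that subsequent tests are non-significant".

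Section 9.7.1.5 then adds: "Testing of all active doses combined compared to vehicle will also be performed". Section 9.7.1.5.1 gives arm-size weights and example code for the combined contrast, whose least-squares means, "treatment differences, 95% confidence intervals, and p-values) will be obtained using estimate statements".

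The general conventions in 9.7.1 supply the defaults: "Statistical tests will be presented as two-sided p-values rounded to four decimal places", and "Unless otherwise indicated, statistical testing will be carried out at the" 0.05 level.

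On the estimands, 9.7.1.5.1 says: "The primary estimands are the treatment differences between SY-201 Ophthalmic Solution arms and vehicle". Section 9.7 states that it covers "additional analyses not explicitly mentioned in the protocol but planned prior to breaking the treatment mask". Protocol section 9.4 plans only comparisons of individual arms with vehicle, so the pooled contrast is an SAP addition.

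**The concern.** The pooled comparison sits in the primary efficacy section, produces p-values and inherits a 0.05 level by default. No visible text ranks it, gives it alpha, or calls it supportive or nominal. Followed literally, the plan runs it even when the very first step (2.0% dose, tCFS) fails. With three arms against one it has more power than a single-dose test if the doses work about equally well. A stopped sequence could therefore sit beside a pooled p<0.05, and the SAP does not say what that would mean. If such a result were presented as an efficacy finding, it would fall outside the 5% error control.

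**Working it through.** **Inputs.** SAP 9.7.2: 45 per arm; tCFS difference 2.0, SD 3.0; symptom difference 1.5, SD 2.4; two-sided 0.05. Allocation is 1:1:1:1, so the pooled weights are one third each. The sign-symptom correlation, and the effects at the individual doses other than the design effect, are not in the documents and are assumed below.

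**1. The plan's own power.** For tCFS the noncentrality is 2.0 / (3.0 × √(2/45)) = 3.162. With 88 df the noncentral t gives 87.9%, matching "a sample size of 45 SY-201-treated subjects versus 45 vehicle-treated subjects will have 87.9% power". For the symptom score, 1.5 / (2.4 × √(2/45)) = 2.965, which gives 83.5%, as stated.

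**2. Pooled power if all doses have the same effect (135 v 45, 178 df).** For tCFS, 2.0 / (3.0 × √(1/135 + 1/45)) = 3.873, power 97.1%. For the symptom score, 3.631, power 95.1%.

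**3. Familywise error under the global null.**
- The six-step sequence makes a false rejection only if step 1 rejects, so its error is 5.0% with or without the pooled test.
- In units of σ²/n, the 2.0% contrast has variance 2, the pooled contrast has variance 1/3 + 1 = 4/3, and their covariance is 4/3. The correlation is (4/3) / √(2 × 4/3) = 0.816.
- The bivariate normal probability that both stay within ±1.96 is 0.9230. If pooled tCFS were also a claim, the error would be 1 − 0.9230 = 7.7%.
- If both pooled endpoints were claims, the error would be 1 − 0.9230 × 0.95 = 12.3% at correlation 0. Simulation gives 11.6% at 0.5 and 10.2% at 0.8.

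**4. How often step 1 fails while pooled tCFS gives p<0.05.** This is P(step 1 fails) minus P(both fail), from the same bivariate normal (SD 3.0 taken as known) with means set by the true effects. Pooled power in the table is from the noncentral t.

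| True tCFS effects at 2.0% / 1.0% / 0.5% (assumed) | Pooled power | Step 1 fails, pooled p<0.05 |
|---|---|---|
| 0 / 0 / 0 | 5% | 2.7% |
| 1.0 / 1.0 / 1.0 | 49% | 18.0% |
| 1.5 / 1.5 / 1.5 | 82% | 18.8% |
| 2.0 / 2.0 / 2.0 | 97% | 9.1% |
| 2.0 / 1.0 / 0 | 49% | 0.2% |
| 2.0 / 1.0 / 0.5 | 61% | 0.6% |
| 2.0 / 1.5 / 1.0 | 82% | 3.0% |

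In the three graded rows the pooled test is weaker than the 2.0% test alone (87.9%), and the awkward outcome is rare.

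**5. The texts side by side.** The error-control statement refers to comparisons within each dose level and counts six hypotheses: three doses by two endpoints, which leaves no room for a seventh. The estimands are by arm. The pooled sentence comes after that closed list and is introduced as something done in addition. Read together, they place the pooled contrast outside the confirmatory family, so its p-value is nominal.

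**The case for a change.** The best case for acting is that the sponsor chose strict control and could say in one sentence whether it binds the pooled test. The SAP does state status elsewhere: it names sensitivity analyses and rules out inferential statistics for compliance. Here it is silent, and its exploratory section is marked not applicable. The display order in 9.7.1 even lists the combined arm first in efficacy tables. Under equal effects, once step 1 has failed, the pooled tCFS test is significant with probability 0.180/0.647 = 28%, 0.188/0.340 = 55% and 0.091/0.115 = 79% at 1.0, 1.5 and 2.0 units, so the question could arise.

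The missing label is real, and writing it down would do no harm. The rest carries less weight. Those conditional figures rest on equal effects, the case that most favours pooling, in a trial titled as a dose-response study. Column order and a default alpha do not add a hypothesis to a family counted as six. The same default also covers non-study-eye results, the earlier visits, the subgroup tests and the sensitivity analyses, and no visible text ranks those either. A plan that names its confirmatory family need not label every test outside it. Some secondary-analysis and subgroup text is blacked out, so silence elsewhere cannot be asserted absolutely.

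**Conclusion.** No change is needed. The six-hypothesis sequence holds its 5% error as written, and the pooled contrast is an ordinary supplementary summary, pre-specified with weights and code in a section that openly allows additions made before unmasking. The 7.7% and the 10% to 12% arise only if pooled results are treated as standalone claims; the latter range also depends on an assumed sign-symptom correlation of 0.8 to 0. The chance of a failed first step beside a significant pooled tCFS result is about 9% to 19% under equal effects of 1.0 to 2.0 units, and about 0.2% to 3% under graded effects with 2.0 units at the 2.0% dose. Both sets of effects are assumptions. An analyst reporting this trial would present the pooled estimate, its 95% interval and a nominal p-value beside the sequence, which is what the text already implies.
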